
## **STUDY PROCEDURES**

**Fasting blood chemistries-** We will obtain blood samples using standard venipuncture techniques for determination of: Fasting serum glucose, HbA1c, and C-peptide (C-peptide may be non-fasting); lipid profile including total serum cholesterol, HDL, LDL, FFA and triglycerides; comprehensive metabolic panel including creatinine, AST and ALT; TSH, renin, angiotensin, aldosterone, ACTH, cortisol, prolactin, and serotonin. Oral glucose tolerance tests and HOMA measure of insulin resistance and beta cell function will also be determined. All of these assays are performed routinely by Sentara Healthcare System. We will also collect samples to assess markers

of inflammation and oxidative/nitrosative stress which include 1) CRP, 2) IL6, 3) TNF alpha, 4) PAI1, SOD, TBARS and ADMA and nitrotyrosine as well as other measures of oxidative/nitrosative stress. We will measure total adiponectin (TA), high molecular weight (HMW) adiponectin, leptin, and their ratios (TA/leptin and HMW adiponectin/leptin). The analyses of plasma markers of inflammation, oxidative/nitrosative stress, neuroendocrine factors and the adiponectin/leptin ratio will be conducted at Vero Science LLC (Tiverton, RI).

***Autonomic function tests- ANS function will be assessed by the measurement of heart rate variability (HRV), which is reduced early in the development of autonomic imbalance in diabetic subjects, and has been associated with increased risk for death after myocardial infarction.*** Power spectral analysis of HRV will be assessed using ANSAR (ANX 3.0 software; ANSAR Group, Inc., Philadelphia, PA). The ANSAR Parasympathetic and Sympathetic (P&S) monitoring method was developed and validated by the Harvard Medical School and Massachusetts Institute of Technology (MIT) Biomedical Engineering department (Akselrod and Aysin). The P&S monitoring method received US FDA Market Clearance in 1995. Time- and frequency-domain analyses will be performed. Time-domain analysis provides a measure of the sympathetic and parasympathetic control of the heart beat (the R-R interval on an electrocardiogram) recorded with maneuvers including deep breathing, Valsalva, and standing from the supine position while frequency-domain analysis is performed under resting conditions. Given their complementary nature both will be utilized in this study. Specifically, total spectral power (TSP) is the average low frequency plus high frequency for each phase during baseline, deep breathing, Valsalva, and postural stimulations. The sample difference of the beat to beat (NN) intervals measures heart rate variability, and was significantly impaired in both diabetic groups when compared to healthy controls in our prior study. The TSP will be calculated, as well as the standard deviation of all normal R-R intervals (sdNN), a measure of both sympathetic and parasympathetic action on HRV, and the root-mean square of the difference of successive R-R intervals (rmSSD), a measure primarily of parasympathetic activity. It is also a measure of changing heart rate variability. ***These time and frequency domain analyses will allow quantification of ANS components, including sympathetic/parasympathetic balance before and after treatment with bromocriptine-QR. We anticipate that autonomic balance, lost early in T2DM subjects, will be re-established with bromocriptine-QR therapy.***

***Sudorimetry- Sweat glands have a preganglionic sympathetic innervation that is regulated by acetylcholine and neuropeptidergic activity. The functional impairment of this system can cause abnormal sweating.*** The Sudoscan (Impeto Medical, Paris, France) will be used to measure the impact of autonomic imbalance on the sweat gland system using reverse iontophoresis. The Sudoscan will employ sudorimetry to assess sweat gland nerve fiber function. Test-retest reliability in 112 healthy controls before and after VO2max test was excellent for the feet (Correlation coefficient of 0.8, p<0.0001). ***Changes in peripheral autonomic function have now been shown to correlate with indices of insulin resistance and inflammation. We will determine if abnormal peripheral autonomic function occurs in newly diagnosed vs. established diabetes and if these are modified by bromocriptine-QR.***

***Skin blood flow (SkBF): methods and procedures-*** *Since activation of the sympathetic arm of the autonomic nervous system has profound effects on microvascular function we will quantify this using laser Doppler techniques. We anticipate that impaired microvascular perfusion seen in newly diagnosed and established diabetes will be correctible with bromocriptine-QR.* Continuous laser Doppler (CLD) will be used to assess skin blood flow in response to several stimuli and allows us to evaluate sympathetic versus neuropeptidergic control of neurovascular perfusion. CLD measurements are a reliable index of SkBF and are uninfluenced by blood flow in the underlying muscle (63). Several pieces of equipment in our lab will be used: the Periflux Master Unit PF4001-2, the Peritemp heating module with sensor PF4005-3, and the (Pressure Unit) (all from Perimed, Inc., Smithtown, NY). After a 30-minute acclimation period 10 minutes of baseline blood flow will be recorded. Following this ten minute period heat will be applied to stimulate WT and NOCI blood flow. WT stimulation will be achieved at 40°C and NOCI stimulation will be achieved by heating the skin to 44°C for 10 and 40 minutes respectively. Skin perfusion will also be measured during cholinergic stimulation.

***Laser Doppler Skin Blood Flow Imaging-*** *Laser Doppler imaging (Moor Instruments Inc., Wilmington, DE) is a standard non-invasive, non-contact technique used to monitor and measure blood flow in very small blood vessels of the microvasculature. Sympathetic overactivity affects the cardiovascular system causing vasoconstriction of small, resistance vessels and we will use this technique as a measure of peripheral sympathetic activity.* Skin blood flow images will be recorded using the Moor LDI2-VR imager. A visible red laser beam will be placed 14 inches from the exposed site and it will take a few minutes to scan over each site being measured. The information collected by the laser is digitally processed into a color coded image displaying the skin blood flow at that site.

***Quantitative sensory tests (QST) -*** Sympathetic activation can be measured by quantifying the sensory perception of heat and cold stimuli. Enhanced responses to these stimuli (hyperesthesia and hyperalgesia) reflect increases in sympathetic tone and will be used as a measure of enhanced peripheral sympathetic activity mediated by the loss of central dopaminergic tone and correctible with bromocriptine. We will use our previously published methods and algorithms for measuring small fiber somatosensory function, including cold and warm thermal sensation, and cold- and heat-induced pain thresholds at the dominant great toe, forearm, and finger in all subjects (64). Generally for each of these non-noxious sensations we will use the method of limits, 4 ascending trials with an inter-stimulus interval randomly varying from 4 to 20 seconds using the Medoc TSA 2001 / VSA 3000 (Medoc Advanced Medical, Minneapolis, MN). Threshold is calculated as the mean stimulus intensity level over all 4 responses.

### **3.2 STUDY DURATION AND DATES**

The duration of this study is expected to be approximately 38 months, with subject recruitment proposed to start in July 2015 and end by August 2018. The actual overall study duration or subject recruitment period may vary.

## 4 SELECTION OF SUBJECTS

### 4.1 NUMBER OF SUBJECTS

A total of up to 80 subjects are planned to be enrolled; At least twenty and no greater than forty early diabetes subjects (diabetes duration of < 4 years) and at least 40 but no greater than 60 subjects with established diabetes (diabetes duration of ≥4 years) will be enrolled in the study.

### 4.2 INCLUSION CRITERIA

1. Diagnosis of Type 2 Diabetes (as defined by the 2004 American Diabetes Association guidelines)
2. Age 30–80 years
3. HbA1c at screening ≤ 10
4. Male or Female (female of child bearing age must use definitive contraceptive therapy)
5. Type 2 Diabetes Mellitus subjects on a stable anti-diabetes regimen of diet and/or metformin alone therapy or on metformin plus an insulin secretion enhancer (sulfonylureas, DPP4 Inhibitors, GLP-1 analogs) therapy for a 60 day period prior to randomization. Subjects must have a documented C-peptide level (either fasting or random) of > 2 ng/ml from the screening visit.

### 4.3 EXCLUSION CRITERIA

1. Presence of type 1 diabetes mellitus.
2. Type 2 diabetes mellitus subjects on insulin.
3. Use of prescription sympathomimetics, ergot alkaloid derivatives, or anti-migraine medications, dopamine2 (D2)-like receptor antagonists (e.g. metoclopramide, domperidone) or systemic corticosteroids
4. Uncontrolled hypertension (systolic BP >160 or diastolic BP > 100 at screening) or a history of orthostatic hypotension
5. History of significant gastroparesis
6. Presence of diabetic retinopathy that is more severe than “background” level
7. Presence of clinically significant peripheral or autonomic neuropathy that is clearly of non-diabetic origin
8. Presence of renal impairment defined by serum creatinine > 1.4 mg/dl if female taking metformin, >1.5 mg/dl. if male taking metformin, and >1.6 mg/dl if not taking metformin
9. History of major macrovascular events such as myocardial infarction or cerebrovascular event such as stroke within the past 6 months. Other exclusions include coronary artery bypass graft or coronary angioplasty in the previous 3 months, unstable angina pectoris (chest pain at rest, worsening chest pain, or admission to the ER or hospital for chest pain) within the previous 3 months, or seizure disorders.
10. Active infection (e.g., HIV, hepatitis), or a history of severe infection during the 30 days prior to screening

11. Major surgical operation during the 30 days prior to screening
12. Cancer, other than non-melanoma skin or non-metastatic prostate cancer, within the past 5 years
13. Uncontrolled or untreated hypothyroidism as evidenced by TSH concentrations >4.8 uU/ml
14. Other serious medical conditions which, in the opinion of the investigator, would compromise the subject's participation in the study, including any concurrent illness, other than diabetes mellitus, not controlled by a stable therapeutic regimen, or conditions or abnormalities (e.g., blindness) that might interfere with interpretation of safety or efficacy data, or history of non-compliance
15. Clinically significant abnormalities on screening laboratory evaluation, unless approved by the Sponsor
16. Abnormalities of liver function defined as any liver enzymes (AST, ALT, SGPT, SGOT) greater than 3 times the upper limit of normal
17. History of NYHA Class III-IV congestive heart failure.
18. Concurrent participation in another clinical trial with use of an experimental drug or device within 30 days of study entry.
19. History (within 3 years) of alcohol or substance abuse, or dementia
20. Pregnant or lactating women. Women of childbearing potential must have a negative pregnancy test at screening. Women who become pregnant will be discontinued from the study.
21. Known hypersensitivity to any of the formulation components
22. Working rotating, varying or night shifts
23. Use of unapproved herbal supplements that may be associated with a risk of cardiovascular events (such as ephedra, yohimbe etc)
24. Subjects who have started therapy with an erectile dysfunction drug within 2 weeks prior to screening; subjects may not begin treatment with an erectile dysfunction drug during the study period; subjects currently taking erectile dysfunction drugs should do so only under medical supervision.
25. Donation of blood in the previous 30 days. Blood donation is also not allowed during the study or for 30 days after completion of the study.

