### Study Duration and Dates

The duration of this study is expected to be approximately 38 months (31-month subject recruitment, up to 3 week screening phase, and 6-month treatment), with subject recruitment to start in June 2015 and the last subject to finish by August 2018.

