## Study Design

This is a single-site, prospective, interventional, twenty-four week, randomized, double blind, placebo-controlled trial with bromocriptine QR in subjects with early diabetes and established T2DM to evaluate its effects on the cardiovascular and peripheral autonomic nervous system, as well as inflammatory markers, the leptin/adiponectin system, hormonal levels of RAS and HPA axis, indices of insulin resistance and glycemic control, and measures of oxidative and nitrosative stress. At least twenty (20) but no more than forty (40) early diabetes subjects and at least forty (40) but no more than sixty (60) subjects with established diabetes will be enrolled in the study.

Entry criteria will be checked at the screening visit. Subjects will be required to be on a stable anti-diabetes regimen consisting of diet and/or oral anti-diabetic agents consisting of metformin alone or metformin plus an insulin secretion enhancer (sulfonylurea, DPP4 Inhibitors, or GLP-1 analogs) for at least 60 days prior to randomization. Following a 2 week lead-in period, subjects will be randomized in a 1:1 ratio to receive UDT (usual diabetes therapy) plus bromocriptine-QR or UDT plus placebo. The circadian timing of the interventional therapy will be within 2 hours of waking in the morning.

Following randomization, subjects will be titrated to the maximum tolerated dose of the study drug (bromocriptine-QR or placebo) over a 4 week period.

Subjects will return at 4 weeks after randomization, at 12 weeks after randomization, and then at study end (week 24 or early termination) for analyses of the primary and secondary endpoints. A primary analysis of the study data will be performed after 12 weeks with a secondary analysis conducted at 24 weeks. Subjects will be contacted 30 days after stopping the study drug to record any adverse events that occurred after cessation.

All visits will be conducted at The Strelitz Diabetes Center, Norfolk, VA.

---

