# STUDY SCHEDULE

Data collected and/or action	Screen	Baseline	Treatment Period (24 weeks)									
	Visit 0	Baseline Visit 1 (Visit 0 + <30 days)	Phone call 1 (Visit 2 + 7 days)	Phone call 2 (Call 1 + 7 days)	Phone call 3 ( Call 2 + 7 days)	Visit 2 Week 4	Phone call 4 Week 8	Visit 3 Week 12	Phone call 5 Week 16	Phone call 6 Week 20	Visit 4 Week 24 (or Early Term)	Phone call 7 Visit 4 +30 days
		Random-ization										
Informed Consent	X											
Entry Criteria	X											
Medical History	X					X		X			X	
Physical Exam	X										X	
Neurological Exam	X										X	
ECG	X										X	
Hematology and chemistry	X										X	
Lipids		X						X			X	
HbA1c	X	X						X			X	
Urine Microalbumin		X						X			X	
Inflammatory oxidative/ nitrosative stress and neuroendocrine Markers		X				X		X			X	
OGTT (with glucose and insulin analyses)		X						X			X	
C-peptide	X							X			X	
HOMA-IR (fasting glucose and insulin)						X						
Autonomic Function Tests		X				X		X			X	
Sudorimetry		X				X		X			X	
Skin Blood Flow		X				X		X			X	
Quantitative Sensory Tests		X				X		X			X	
Study Drug instruction (first dose next AM)		X										
Study Drug Titration reminder			X	X	X							
AE/SAE query/ Study Drug assessment			X	X	X	X	X	X	X	X	X	
Final follow up for AE/SAE resolution												X
Concomitant meds			To be assessed throughout the study									
Adverse Events			To be assessed throughout the study									
Serious Adverse Events			To be assessed throughout the study Report serious adverse events to sponsor within 24 hours									
Mandatory Contact			Weekly titration phone contacts as described in the protocol									

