## **7 OVERVIEW OF DATA COLLECTION AND STUDY PROCEDURES**

### **7.1 STUDY PROCEDURES AND SCHEDULES**

The study will consist of a screening visit, followed by visits at week 0 (baseline), week 0 + 1-3 days for study drug initiation, week 4, week 12 and week 24 or early termination. There will be a final telephone contact 30 days after discontinuation of study drug to assess for new adverse events or for resolution of ongoing adverse events.

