### **7.2 DESCRIPTION OF STUDY DAYS**

#### **7.2.1 Screening - Visit 0**

Screening of subjects will occur at Visit 0. Potential subjects will be instructed to arrive at the screening visit having fasted from midnight the night before. Consent form must be signed prior to conduct of any study procedures including screening tests for eligibility.

- Each subject will be assigned a study subject number\*
- Assessment of inclusion/exclusion criteria will be performed\*
- Medical history, including demographic and background assessments will be documented in the CRF\*
- Routine physical examination will be performed\*
- ECG test will be performed\*
- Blood will be taken for the determination of HbA1c, clinical chemistry variables (and serum pregnancy test for women of child-bearing potential), hematology, (see study schedule).
- A C-peptide level (fasting or random) will be measured and must be > 2 ng/ml for continuation in the trial.\*
- Total amount of blood drawn at this visit will be approximately 30 ml.

\* These procedures may be performed at the same visit the consent form is signed or at Screening Visit 0.

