## 7.2.2 Study Days – Treatment Period

### 7.2.2.1 Baseline – Visit 1 (Post Visit 0 + <30 days)

Subjects will be instructed to arrive having fasted from the night before this visit.

- Sudorimetry
  - Sudoscan
- Autonomic Function Tests
  - Heart Rate Variability (HRV)
- Blood will be taken for the determination of HbA1c, lipids, neuroendocrine factors, inflammatory markers and oxidative/nitrosative stress markers
- Urine will be obtained for measurement of microalbumin
- An OGTT will be administered and OGTT glucose and insulin levels will be obtained at 0, 30, 60, 90 and 120 minutes post-glucose challenge.
  -
- Skin Blood Flow (SkBF)
  - Continuous Laser Doppler
- Quantitative Sensory Tests (QST)
- Total amount of blood drawn at this visit will be approximately 50 ml.
- Subjects will be randomized per Eastern Virginia Medical School SOP II-805:
- Subjects will be provided with instructions on starting study drug the morning after this visit.

 
• Sub-investigator
 
• Research coordinator
 
	
Randomize and blind an investigational drug by assigning each patient/subject a study number in the order they are recruited. The patients are randomized using a randomizing web site at (www.randomizer.org). The randomized patient numbers are recorded in the grid in Attachment A, Blinding/Randomization Code. This code is then placed in an envelope and sealed. Place a label (Attachment B, Blinding/Randomization Individual Subject Envelope Label) on the envelope. This envelope should remain sealed until the study is concluded.

 
• Sub-investigator
 
• Research coordinator
 
	
Complete a blinding/randomization patient form, (Attachment C) for each patient and seal the individual envelopes. The outside of the envelopes should contain patient numbers for identification purposes. This allows the research coordinator to break the individual blind in emergency situations without compromising the rest of the blinding data.
 
Document all circumstances appropriately and place in the study binder.
 
Report all serious adverse events to the FDA and IRB. More general guidelines on adverse event reporting can be found in SM-404 and II-806 of these SOPs.

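### Pregnancy is tested only at screening, up to 30 days before the first dose (32 under section 7.1), and the duty to report a pregnancy stops at the last dose; a low-priority gap that is cheap to narrow

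*Protocol*

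**What the plan says.** **Testing.** Protocol 4.3 item 20 excludes "Pregnant or lactating women" with no time limit, and continues: "Women of childbearing potential must have a negative pregnancy test at screening. Women who become pregnant will be discontinued from the study". Section 7.2.1 carries this out by adding a "serum pregnancy test for women of child-bearing potential" to the Visit 0 bloods. The lists for Visit 1 (7.2.2.1), Visit 2 (7.2.2.5), Visit 3 (7.2.2.7) and Visit 4 (7.2.2.10) contain no pregnancy test.

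**Timing.** The protocol describes the time from screening to first dose in several ways:
- Outline, Study Design: "Following a 2 week lead-in period, subjects will be randomized in a 1:1 ratio".
- Outline, Study Duration and Dates: "up to 3 week screening phase".
- Study Schedule: "Baseline Visit 1 (Visit 0 + <30 days"; the heading of 7.2.2.1 gives the same window.
- Section 7.2.2.1: "Subjects will be provided with instructions on starting study drug the morning after this visit". The Study Schedule also puts the first dose on the next morning.
- Section 7.1: "week 0 + 1-3 days for study drug initiation".

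**Reporting.** Section 8.1.3 requires immediate notice to the sponsor of a pregnancy in a female subject, or in a male subject's partner, if it is diagnosed while study treatment is being given. Section 8.2 keeps adverse-event observation open until 30 days (± 3) after the last dose. The final call (7.2.3) asks about adverse events only.

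**Other safeguards.** Section 4.2 item 4 requires definitive contraception. Section 9.1 requires withdrawal from study drug on pregnancy, or on stopping contraception in order to conceive.

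**The concern.** The protocol makes pregnancy an exclusion, a mandatory stop and an immediate report. Two of its procedures fall short of those rules.

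First, nothing scheduled between Visit 0 and the first dose would detect a new pregnancy. Contraception lowers the chance of one but detects nothing, and the exclusion and withdrawal rules act only once the pregnancy is known. A woman with an unrecognised pregnancy can start blinded drug.

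Second, the trigger in 8.1.3 is the date of diagnosis, not exposure. A pregnancy conceived in the last weeks on drug and found after Visit 4 was exposed but lies outside the wording, so it may never reach the exposure follow-up that 8.1.3 sets up.

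At stake are subject safety and the completeness of the safety record. The two gaps have different mechanisms and different fixes.

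**Working it through.** **Step 1: days from the Visit 0 test to the first dose.** The protocol states no such interval, so there is no figure to reproduce. Longest interval = longest time from Visit 0 to Visit 1 + days from Visit 1 to drug start. Less than 30 days means at most 29.

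| Wording for Visit 0 to Visit 1 | Next-morning start | Start up to 3 days later (7.1) |
|---|---|---|
| Less than 30 days (Study Schedule, 7.2.2.1) | 29 + 1 = 30 | 29 + 3 = 32 |
| Up to 3 weeks (outline) | 21 + 1 = 22 | 21 + 3 = 24 |
| 2-week lead-in (outline, 3.1) | 14 + 1 = 15 | 14 + 3 = 17 |

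The last row assumes that the lead-in starts at Visit 0. If the lead-in sets no minimum from Visit 0, the interval could be shorter still. The Study Schedule and 7.2.2.1 agree on both the window and the next-morning start, so 30 days is the best-supported maximum. The 32 rests on one phrase in 7.1.

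**Step 2: what a Visit 1 test changes.** The time from last test to first dose becomes 1 to 3 days. That is not the period at risk. If a urine test cannot detect a conception in the last L days before it, an undetected conception can still fall in the last L + 1 to L + 3 days before dosing. Of conceptions dated after Visit 0, the test can catch those from 29 − L days under the less-than-30-day window, or 14 − L under the lead-in. The documents give no L; at L = 14 the second figure is zero. The counts in step 3 are therefore conceptions, not cases prevented.

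**Step 3: size (illustration; all rates assumed).** Assumptions: 5 to 15 women of childbearing potential among the 80 subjects; 1% to 9% yearly contraceptive failure, spread evenly over the year; 2 to 6 weeks (14 to 42 days) from conception to recognition. Half are on active drug (1:1 randomization). Expected active-arm cases = 0.5 × women × yearly rate × days ÷ 365.

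Conceived between test and first dose:
- Lowest: 0.5 × 5 × 0.01 × 15 ÷ 365 = 0.001
- 15 women, 1%: 0.5 × 15 × 0.01 × 32 ÷ 365 = 0.007
- Highest: 0.5 × 15 × 0.09 × 32 ÷ 365 = 0.059

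Conceived on drug, diagnosed after the last dose:
- Lowest: 0.5 × 5 × 0.01 × 14 ÷ 365 = 0.001
- 15 women, 1%: 0.5 × 15 × 0.01 × 42 ÷ 365 = 0.009
- Highest: 0.5 × 15 × 0.09 × 42 ÷ 365 = 0.078

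At a 42-day lag, some of the last group would be diagnosed more than 30 days after the last dose, so 0.078 is on the high side for the follow-up period. The chance of no case at the highest inputs is exp(−0.059) = 0.94 and exp(−0.078) = 0.93. Required definitive contraception points to the low end of the failure range. Partners of male subjects are not counted.

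**Step 4: whether other text closes the reporting gap.** Uncomplicated pregnancy is not named in the adverse event definition (8.1.1). The serious-event list (8.1.2) covers a congenital anomaly, not the pregnancy itself. Section 8.3 allows expedited reports without an adverse event in other situations, but refers back to 8.1.3 for them. None of this creates a duty to report a pregnancy first diagnosed after the last dose.

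**The case against.** A single serum test at screening is a deliberate choice, backed by contraception, exclusion, withdrawal rules and frequent contact after the first dose. Expected cases are close to zero, the inputs behind any count are assumed, and a urine test would miss some of the conceptions at issue. On reporting, the form named in 8.1.3 concerns exposure through a parent, so the intent may be wider than the wording. Every subject is called after stopping drug, and under 8.2 a possibly related serious event found after the observation period is still raised with the sponsor. The form itself, the reporting instructions and the consent document were not available.

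Most of this stands, and it sets the priority low. It does not remove either gap: none of these safeguards detects an unrecognised pregnancy before the first dose, and 8.1.3 followed literally omits an exposed pregnancy found just after the last one.

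A reader might infer more than the documents support:
- That known pregnancies could be dosed. Item 20 excludes pregnant women without a time limit, so one known at Visit 1 bars dosing.
- That every subject waits 15 to 32 days. Those figures are maxima under conflicting wordings, not one range.
- That the missing row in the Study Schedule proves the test was omitted. The Schedule has no pregnancy row even for Visit 0, where a test is required; the point rests on the visit lists.
- That fetal harm is shown. The documents give no fetal-risk data.

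**Conclusion.** The point holds as two narrow, low-priority gaps. The only scheduled test can precede the first dose by up to 30 days (32 under 7.1), and by less if the lead-in or 3-week wording governs, so an unrecognised pregnancy can be dosed. A pregnancy conceived on drug and diagnosed in the 30 days after the last dose has no explicit reporting duty.

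The intervals follow from the protocol's own windows. The case counts rest wholly on assumed inputs, and zero is the most likely count throughout. The reporting gap is judged on the protocol wording alone; sponsor instructions not seen here may already cover it. Endpoints, sample size, power and the analyses in the SAP are not affected.

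**What to change.** 1. For women of childbearing potential, require a negative urine pregnancy test at Visit 1 before study drug is given out, using the urine already collected for microalbumin. Add a pregnancy-test row to the Study Schedule for Visits 0 and 1.
2. Reword 8.1.3 to cover any pregnancy with possible exposure during treatment, in a subject or a male subject's partner, diagnosed up to the end of the 8.2 observation period.
3. Add a question on pregnancy in subjects and partners to the final call (7.2.3).

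The outline has the last subject finishing by August 2018. If dosing is over, the second gap can still be addressed by asking whether any exposed pregnancy was diagnosed after the last dose.

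The cost is a small amendment, one inexpensive test per woman concerned, one sentence and one question, plus some extra reporting and consent and follow-up work for partners.
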